Recruitment. Eligible participants will contact our study in response to 1) flyers posted in VA mental health, primary care, and alcohol and substance use treatment programs; 2) advertisements in print and web-based media; 3) referrals from VA primary care, SAMI, PTSD, and other psychiatry clinics and 4) from other research studies who's participants provided consent to contact. Following verbal consent, potential participants will undergo an initial screening that takes approximately 30-45 minutes to complete. The screening, used in the PI's current CSR&D merit study, is intended to detect clinically significant alcohol use and PTSD symptoms. It consists of screening items from the SCID [52] and the Posttraumatic Stress Disorder Checklist-5 [PCL-5; 53] for disorders that are part of the inclusion and exclusion criteria. Those who meet study criteria will attend an in-person interview where they will sign informed consent documents and take part in a baseline assessment (see measures in 9.8.). Following baseline assessment, participants will have the opportunity to meet with a research study therapist to talk about their goals for taking part in the study treatments and the pros and cons of taking part in the study. Following the session, participants who choose to proceed with study participation will be randomized to the intervention or control condition. Random permuted blocks will be used which ensure exactly equal treatment numbers at certain equally spaced points in the sequence of patient assignment. A computer-generated randomization sequence will be provided by our and held by [name] study pharmacist. *Randomization will be stratified by whether or not the participant is on a anti-relapse medication. It is expected that randomization will balance out severity of PTSD symptoms, severity of alcohol use, and functional impairment, and this will be assessed in analyses excluded.*

Women and Minorities

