Standard Pharmacotherapy. Pharmacological treatment will be provided at no cost to the proposed project. The VA follows treatment guidelines that require standardized prescribing practices for individuals with PTSD, depression, and AUD. We expect at least 85% of

participants will be receiving medications based on these guidelines. We recognize that pharmacotherapy and changes in medications will be an uncontrolled source of variance but expect that any changes will be similar across treatment conditions and thus balanced by randomization. We considered recruiting participants who were not on medication or asking participants to be medication stable prior to study entry. However, psychotropic medications have well documented effectiveness for the treatment of PTSD and withholding such medication would be inappropriate for this high-risk population. The only exception is if participants are on addiction medications they will be asked to stay on a stable approved dose at least two weeks before starting the study drug and throughout the study. Study coordinators will record from VA medical records and patient self-report all treatment (psychotherapy and medication) in which Veterans participate in the VA. Participants will also be asked about treatment outside of the VA. We will compare treatment as usual between our two conditions and, if differences in any variables are found, include these as covariates in analyses.

Blind. All investigators, clinicians, and study staff will be blind to treatment condition. Only the research pharmacist will know to which group participants have been randomized. The success of the blinding procedure will be evaluated by having the rater guess the patient's assigned treatment condition after each assessment. If indicated, participants will be asked to go through detoxification prior to beginning the study. Detoxification programs are available on inpatient and outpatient bases through programs funded by the San Diego VA.

Sources of Materials: The data relevant to the proposed project will be gathered strictly for research purposes. Blood and urine specimens obtained are for clinical and research purposes only. Sources of research data will be demographic data collected from participants recruited for this study, ratings from independent clinical evaluators, patient self-reports, toxicology screens, and through VA CPRS chart review.

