- **Data Management.** In the initial 3 months, data management procedures will be developed and implemented. Data entry and quality assurance will be ongoing during enrollment, with validation and double-entry procedures in place to ensure accurate data entry. Study staff will be trained to limit missing data by checking questionnaires

immediately and prompting for additional response and re-contacting participants if necessary. Study staff will attempt to collect all post-randomization data regardless of treatment attrition.

- **Statistical Analysis.** Data analysis will occur in a staged approach, moving from initial descriptive analyses to hypothesis tests. Descriptive statistics and plots will summarize and assess distributional properties of key variables. Randomized groups will be compared on baseline demographic and clinical variables using analysis of variance, 2, or Wilcoxon-rank sum tests. Any baseline variables potentially confounded with treatment condition will be incorporated in the primary analyses as covariates. Outliers will be assessed and variables whose distributions depart significantly from normality will be transformed.

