- **Primary Aim Analysis.** As stated in Aim 1, we will evaluate the efficacy of PE+TOP, as compared to PE+PLA, in percent heavy drinking days (PHDD) among Veterans with comorbid AUD/PTSD at post-treatment and 3- and 6-month follow-up. The statistical model will be a generalized linear mixed model with a log link and gamma distribution variance function. If the over-dispersion parameter is close to zero a Poisson regression model will also provide equivalent model fit. The model will include a factor for treatment condition (PE+TOP, PE+PLA) and a linear term for time (baseline, post-treatment, 3, and 6 month follow-up). This model can be expanded to determine an adjusted intervention effect by including covariates such as gender and era of service. The primary test of treatment effect will be a group x time interaction. This flexible analytic method provides maximum likelihood parameter estimates based on all of the available data, allowing for the inclusion of cases with missing data and the modeling of the covariance error structure of the data across the

assessment points [90]. If the extent of missing data is small and the data appear to be consistent with a missing-at-random model, we will also carry out maximum-likelihood based on a “completer-analysis” using the observed data.

- **Secondary Aim Analyses.** As stated in Aims 2 and 3, veterans in PE+TOP, compared to PE+PLA, will show greater improvements in PTSD, depression symptoms, functional impairment and quality of life at post-treatment and 3- and 6-month follow-up. We will first examine the relationships among these outcomes to determine if composite scores should be created from highly correlated variables. This will help to reduce the number of statistical tests. The statistical model for these analyses will be random effects regression models as described in the primary aim analysis section, using identity link for Gaussian distributed linear variables and log or logit link functions for discrete or skewed outcome variables. These analyses would be in an intent-to-treat framework using maximum likelihood as before.

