- 11) Individuals with clinically significant renal disease and/or impaired renal function, as defined by clinically significant elevation of blood urea nitrogen (BUN) or creatinine or an estimated creatinine clearance of < 60 mL/min, can be included with physician approval, however the dosing schedule and maximum dose will be adjusted in accordance with FDA prescribing guidelines,
- 12) if individual is on another addiction medication, they should be on a stable approved addiction medication dose (at least two weeks before starting study drug) throughout the study,
- 13) are capable of giving informed consent.

Exclusion criteria are:

- 1) Subjects known to have clinically significant unstable medical or psychiatric conditions, where participation is deemed by investigators and study physicians to be risky, including but not limited to:

-AST and/or ALT >5 times the upper limit of the normal range and/or an increased serum bilirubin >2 times the upper limit of normal.

-Seizure disorders

- 2) have been treated with Topiramate for any reason in the past and discontinued the drug due

to hypersensitivity reaction

3) in the opinion of the investigator, should not be enrolled because of the precautions, warnings, or contraindications listed on the Topiramate package insert, (e.g., certain types of glaucoma),

4) are pregnant, lactating, or plan to become pregnant during the period of participation in the study

5) in the judgment of the investigator, represent a significant risk of suicidal or homicidal behavior

Women and Minorities

Women comprise 11% (e.g., SAMI clinic) to 60% (Military Sexual Trauma clinic) of the Veterans seen in the clinics from which we will be recruiting, and approximately 24% of Veterans in the program are minorities. Consistent with SAMI demographics as a whole, 10% of participants in our current Merit study over the past 3 years have been women. We have been able to obtain 26% Hispanic, 16% African American, and 20% other ethnic groups, for a total of 52% from minority groups. We will continue attempts to oversample these groups to obtain adequate recruitment of females and minorities to examine effect sizes for these groups relative to male and Caucasian counterparts.

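### Randomisation is stratified by anti-relapse medication, but the primary model leaves the stratum out; the likely cost is small, and pre-specifying the stratum and its interaction with time needs no new data

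*Combined protocol and SAP*

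**What the plan says.** **Allocation.** Section 9, Recruitment, describes permuted-block randomisation with one stratification factor: "Randomization will be stratified by whether or not the participant is on a anti-relapse medication". The term is not defined and no list of drugs is given.

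**Eligibility and concomitant treatment.** Inclusion criterion 12 in Section 10 uses another term: "if individual is on another addiction medication, they should be on a stable approved addiction medication dose". Standard Pharmacotherapy in Section 9 has the same term and the same stability requirement: "The only exception is if participants are on addiction medications they will be asked to stay on a stable approved dose". It is not defined there either.

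**Primary model.** The Primary Aim Analysis states: "The model will include a factor for treatment condition (PE+TOP, PE+PLA) and a linear term for time". It continues: "The primary test of treatment effect will be a group x time interaction". An optional extension is allowed: "This model can be expanded to determine an adjusted intervention effect by including covariates such as gender and era of service". The stratification factor appears in neither.

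**Conditional covariates.** The Statistical Analysis bullet says: "Any baseline variables potentially confounded with treatment condition will be incorporated in the primary analyses as covariates". Standard Pharmacotherapy adds treatment-as-usual variables as covariates if the two conditions are found to differ on them. Medication status is a named covariate only in the genetic analysis.

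**The concern.** Stratified allocation makes the arms more alike on the stratum than simple randomisation would. If the stratum predicts the outcome, an analysis that ignores it counts between-stratum variation as noise in the treatment contrast, although the design has already removed it. The standard error is then too large and the test conservative. Being on a medication intended to prevent relapse could well be related to heavy drinking, so the question applies here.

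Power is tight. The Power analysis accepts 72% on a one-tailed test because the 192 participants needed for a two-tailed test at 80% are judged infeasible. Precision available from data already recorded should not be left unused by default.

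There is also a matter of pre-specification. With the stratum unnamed, its inclusion depends on an imbalance check or on an open list of optional covariates, so the choice could be made after the data are seen.

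**Working it through.** **1. The plan's own power figure.** Inputs from the Power analysis and Section 10: d = 0.406, 60 per arm. Alpha is not stated; 0.05 is assumed.

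- Non-centrality: 0.406 / √(1/60 + 1/60) = 2.224.
- One-sided power: Φ(2.224 − 1.645) = 0.719 (0.714 with the t distribution), against the stated 72%.
- Two-sided total for 80% power: 2 × 96 = 192, as stated.
- Two-sided power at d = 0.516: 0.807 (0.800 with the t distribution), against the stated 80%.

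These figures reproduce, and none assumes adjustment for the stratum.

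**2. Post-treatment comparison with a balanced stratum.** Let R² be the share of outcome variance explained by the stratum. The documents give neither the proportion on such medication nor its link with drinking, so R² is an assumed range. As a guide, with a proportion q on medication and an outcome difference of δ SD, R² = q(1−q)δ² / (1 + q(1−q)δ²):

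- q = 0.3, δ = 0.5: 0.0525 / 1.0525 = 0.050.
- q = 0.5, δ = 0.8: 0.16 / 1.16 = 0.138.

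With exact balance, one-sided, normal approximation:

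- actual alpha of the unadjusted test = 1 − Φ(1.645 / √(1−R²))
- unadjusted power = Φ((2.224 − 1.645) / √(1−R²))
- adjusted power = Φ(2.224 / √(1−R²) − 1.645)

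| R² | Actual alpha, unadjusted | Power, unadjusted | Power, adjusted | Points forgone |
|---|---|---|---|---|
| 0.02 | 0.048 | 72.07% | 72.62% | 0.6 |
| 0.05 | 0.046 | 72.37% | 73.78% | 1.4 |
| 0.10 | 0.041 | 72.91% | 75.78% | 2.9 |
| 0.15 | 0.037 | 73.50% | 77.85% | 4.4 |

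**3. The stated primary test, group by time.** This was simulated with a Gaussian random-intercept model: 60 per arm, four equally spaced visits, intraclass correlation 0.5, 30% in the stratum, two-sided, 4,000 runs. The treatment slope was 0.15 SD per visit, a value set for the simulation and not taken from the plan.

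- *Stratum shifts the level only (0.7 SD).* Power is 72.4% without a stratum-by-time term and 72.4% with it; alpha is 0.049 and 0.050. A constant shift cancels within each participant.
- *Stratum shifts the slope (0.2 SD per visit).* Without the stratum-by-time term, alpha is 0.043 and power 72.9%. With it, alpha is 0.046 and power 73.9%.

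The Monte Carlo standard error of an alpha near 0.05 is √(0.05 × 0.95 / 4000) = 0.003, so a direct calculation is a useful check. With visits coded −1.5 to 1.5, the squared times sum to 5. The omitted slope raises the residual variance from 0.5 to (358 × 0.5 + 120 × 0.3 × 0.7 × 0.2² × 5) / 358 = 0.514, a ratio of 1.028.

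- Alpha without the term: 2 × (1 − Φ(1.96 × √1.028)) = 0.047.
- Non-centrality: 0.15 / √(0.5 × (2/60) / 5) = 2.598.
- Power with the term: Φ(2.598 − 1.960) = 73.8%.
- Power without it: Φ(2.598 − 1.987) = 72.9%.

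The cost in this example is about one point of power, and the shortfall in alpha is slight.

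**4. Would the existing rules add the stratum?** Both conditional rules need a difference between arms. The allocation method is described so: "Random permuted blocks will be used which ensure exactly equal treatment numbers at certain equally spaced points". Applied within strata, that keeps the arms close on this factor. The better stratification works, the less likely either rule is to bring the factor in.

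**The case against.** **The effect on the stated primary test may be nil.** This stands for a stratum that only shifts the level of drinking. The figures in step 2 belong to a post-treatment contrast, which is the basis of the plan's power calculation but not its named primary test. Adding a stratum main effect alone would do almost nothing for group by time.

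**A reader might infer that the trial wastes the balance it creates.** The documents do not support that. Allocation balances the arms whether or not the factor is modelled, and in a linear model the estimate is not biased by leaving it out. What is at stake is some precision and the exact level of the test.

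**A reader might infer that eligibility defines a different class of drugs from the stratum,** for instance one that takes in treatment for opioid or nicotine dependence. Neither term is defined, and they may mean the same drugs. Criterion 12 can be read simply as any addiction medication besides the study drug. What can be said is that the wording is undefined and inconsistent.

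**Gender and era of service** are optional examples in an open list, not a standing adjustment that displaced the stratum. The plan therefore does not forbid including the stratum; it leaves it unspecified.

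**The upper assumptions are generous.** A stratum difference of 0.8 SD is about twice the 0.406 expected of topiramate itself (0.8 / 0.406 = 1.97), so the lower rows of the table are the more cautious guide.

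**Conclusion.** The point holds as a modest, low-cost improvement. The plan stratifies on a factor that its primary model does not name, and its imbalance-triggered rules are unlikely to add it.

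The consequence is mild conservatism, not bias. For a post-treatment contrast, one-sided alpha is about 0.048 to 0.037 in place of 0.05, and about 0.6 to 4.4 points of power are forgone, for an assumed R² of 0.02 to 0.15. For the stated group-by-time test the loss is near zero unless the stratum affects change over time; the illustrative case gives 72.9% against 73.9% power and a simulated alpha of 0.043 (0.047 by direct calculation).

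These results rest on an alpha of 0.05, exact balance within strata, an assumed prognostic strength, and a Gaussian approximation to the planned gamma model with log link. The documents do not say how common such medication is or how it relates to drinking.

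**What to change.** In the Primary Aim Analysis, and in the Secondary Aim Analyses that build on it, pre-specify the stratification factor as randomised, together with its interaction with time for as long as group by time is the primary test. Gender and era of service may remain optional covariates.

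As a supporting clarification, state in Recruitment which medications set the stratum. If randomisation has begun, which the documents do not say, this should be the rule the pharmacist actually applied, so that the analysed stratum matches the allocations already made. Then reconcile that wording with the term used in Standard Pharmacotherapy and in inclusion criterion 12, without changing the scope of the stability rule: the stratum needs its own definition and a cross-reference, and eligibility need not be redefined.

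The cost is two model terms with 120 participants and edits to a few paragraphs. No new data are needed, because medication status must already be known at allocation and treatment is already recorded.

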All participants will receive PE psychotherapy for PTSD. Although several treatments have been found effective in treating PTSD, we have selected PE based on its particularly strong empirical record and its appropriateness given study aims. The evidence for PE efficacy is greater than that for any other PTSD intervention, and treatment effects are generally maintained during follow-up. Thus, the safety and tolerability of PE is well documented for patients with and without AUD, and, because of [name] and other investigators' experience administering and disseminating PE for patients with and without AUD, the study team is exceptionally well prepared to utilize this intervention.

PE [19] includes breathing retraining; psychoeducation; prolonged, repeated exposure to trauma memories (imaginal exposure); processing of trauma related material that emerges during exposure; and repeated real life exposure (in-vivo) to trauma-related avoided situations. Participants will practice in vivo exposure and listen to audio of imaginal exposures between sessions. PE is delivered over 12 weekly sessions. Ideally, participants attend therapy each week; however, participants sometimes miss appointments. Therefore, participants will have up to 16 weeks (while they take TOP or PLA) to complete the 12 sessions. Consistent with our other studies of PE with AUD/PTSD samples, during the first five minutes of session, therapists will query participants about cravings and alcohol use since the last session and check in with participants regarding progress toward their alcohol use goals. This 1) allows therapists to assess whether there is increasing alcohol or other substance use that may necessitate referring the Veteran to a higher level of care (see Human Subjects), 2) gives therapists important clinical information about whether participants are using alcohol in a way that may interfere with PE mechanisms (e.g., drinking

just before or after exposure assignments), and 3) gives therapists the ability to support participants in achieving their alcohol use goals in a fashion consistent with the approach used by study physicians at the medication appointments [63].

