- **Missing Data.** The primary outcome will be tested using an intent-to-treat framework. If, the extent of missing data is small and the data appear to be consistent with a missing-at-random model (MAR) [84], then the maximum likelihood analysis using all randomized cases and the observed data is an appropriate method for handling the missing data [85]. In the MAR model the missingness can be a function of the observed covariates and observed outcomes. If the missingness is related to the unobserved outcome, then the missing values are considered missing not at random (MNAR). However, the MAR assumption has been shown to be plausible even in studies such as substance abuse in adolescents [86]. The critical element when conducting MAR-based analyses is to include covariates related to the missingness in the statistical model [87]. As a check on the sensitivity of our conclusions to the assumption that the missing data are MAR we will conduct pattern-mixture modeling, which is appropriate with data is likely MNAR [88, 89]. In these models participants are categorized into groups based on patterns of missing data over time. Missing data pattern groups are then included as covariates in the statistical model and the effect of missing data on parameter estimates can be determined. Parameter estimates can be averaged over the missing patterns to adjust for biased estimates.

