Measures of Mechanism and Mediation. The Expectancy of Therapeutic and Medication Outcome [ETO; 81], This measure will be used to understand treatment credibility and participant's beliefs about how much the study treatments will help their trauma symptoms and alcohol problems. The Expectancy of Therapeutic and Medication Outcome is a 22-item self-report scale to evaluate participant's expectancies and beliefs about treatment credibility. It will be administered in Session 1. Questions are rated on a Likert-type scale (0-8).

The Additional Treatment Inventory (ATI) assesses additional psychiatric medications and psychotherapy sought during and after the completion of study treatment. The Client Satisfaction Questionnaire [CSQ; 82] is an 8-item self-report scale measuring satisfaction with treatment that will be used to measure participants' satisfaction with the interventions. Participants will also complete content specific questionnaires for each intervention at the end of each session. Process measures will include number of sessions attended, homework compliance, and tardiness.

Medication Adherence and side effects. We will use interview and pill counts as the primary assessments to measure adherence. To expand upon the reliability of this information, medication will be dispensed weekly in vials showing morning and evening doses separately. Our staff will review this information with the participant at each weekly visit and we will supplement pill counts with the ACTG Interview of Antiretroviral Medication Use which was developed by the Adult AIDS Clinical Trials Group to assess in detail HIV medication adherence over the previous four days and takes about 10 minutes to complete [83]. The measure was modified for the current study to assess adherence to TOP. Side effects will be collected weekly using a checklist of 18 common AE's associated with TOP as indicated in the FDA-approved labeling for TOP [12].

Cannabis assessment (frequency and use): A single item assessing frequency of use for different forms of cannabis. To better assess for participants' cannabis use.

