The DTS (Simons & Gaher, 2005) is a 15-item self-report measure that assesses the ability to experience and tolerate aversive emotional states using a Likert type scale (1= Strongly Agree to 5 = Strongly Disagree). Specifically, the DTS measures the tolerance of aversive emotional states, appraisal of distress, attention absorbed by distress, and efforts to regulate distress. The DTS displays good internal consistency, convergent and discriminant validity, and temporal stability.

Medication Adherence form: A 2 item questionnaire regarding medication adherence

Coronavirus Stressor Survey - This survey will be used to determine stressors patients face during the coronavirus pandemic. This assessment will be given at all assessment timepoints. (McLean, C. P. & Cloitre, M., 2020).

COVID Impact on Therapy Participation survey - This survey is meant to measure how COVID-19 has impacted participants ability to participate in evidence-based psychotherapy research at the VA.

Section 9.9 Data Safety Monitoring Board or Plan

9.9) Provide a Data Safety Monitoring Plan (DSMP) or the details of a Data Safety Monitoring Board.

Data Safety Monitoring (DSM). DSM will include periodic review and reporting of participant accrual, adverse event rates, treatment compliance, and drop-out rates. Study termination will be triggered by excessive drop-outs or adverse events. Adverse events includes 1) need to break confidentiality, 2) loss of data, 3) inadvertent harm caused by study participation, 4) patient suicidality. If treatment is needed during the follow-up phase due to increased alcohol consumption or serious psychiatric/medical symptoms, patients will be referred to appropriate treatment and followed by the PIs and study therapist until treatment is initiated. Adverse events will be reported to the San Diego VA's IRB and the VA ORD (serious adverse events within 48 hours) and clinically managed as appropriate. A summary of all adverse events will be submitted to VA ORD and RR&D annually. The PI (licensed in the state of California) will be available by phone 24-hours a day. The PI will be responsible for initial determination of serious adverse events from non-serious adverse events. This study would report to the VA DSMB and follow all criteria for reporting.

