2) To minimize the risk of patient discomfort, confidentiality will be stressed, participants will be offered breaks as needed, they will be informed that they have the right to refuse to answer questions or to terminate their participation in the study at any time without prejudice, and everyone who interacts with participants will be trained and supervised. Clinical staff will be available at each location if immediate in-person evaluation is required for medical or mental health issues.

3) and 4) To minimize the risk of patients becoming more anxious or depressed or increase drinking, every patient will be given a 24-hour contact phone number to call in the event of increased symptoms. During each assessment, the independent evaluator (IE) will assess for any major changes in health (e.g., overnight hospitalizations), possible adverse events, suicidal ideation, and general well-being. Study clinicians, during medication and psychotherapy visits, will assess for clinical worsening as part of the session protocols. If worsening symptoms are detected at any visit, a study clinician will be available to evaluate the patient and refer to appropriate treatment if needed. When in doubt, the decision whether continued participation in the study is safe and clinically warranted will always be on the side of patient safety. If a therapist or assessor identifies worsening substance use, the study investigators will evaluate whether best clinical care indicates a need for continuation in the study or more intensive SUD treatment. Participants will complete the Substance Use Inventory (SUI) at each session which will show worsening substance use. Therapists will be trained to contact the PI if a participant reports three or more days per week of alcohol use with more than four standard drinks or three or more days of illicit drug use in a week. If more intensive treatment is appropriate, we will assist the participant in obtaining the appropriate treatment. If the treatment is counter to study criteria, then we will discontinue the participant from the study following a final evaluation.

Adverse events, including those unlikely to be the result of participation in the research (e.g., hospitalization due to an automobile accident), will be monitored at every study contact, including medication, psychotherapy and assessment visits. They will be reported to the appropriate human subjects committees as per policy.

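### The treatment-as-usual covariate rule is not limited to pre-randomisation values, so it permits adjustment for care that the study drug may have changed

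*Combined protocol and SAP*

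**What the plan says.** The rule is in Section 9, Standard Pharmacotherapy: "We will compare treatment as usual between our two conditions and, if differences in any variables are found, include these as covariates in analyses". It gives no time point, no threshold for a difference, and no list of the analyses it covers.

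The same paragraph shows that care during the study is in view. It says that "Study coordinators will record from VA medical records and patient self-report all treatment (psychotherapy and medication) in which Veterans participate in the VA", and the authors accept that "pharmacotherapy and changes in medications will be an uncontrolled source of variance but expect that any changes will be similar across treatment conditions". In Section 9.8 the Additional Treatment Inventory "assesses additional psychiatric medications and psychotherapy sought during and after the completion of study treatment", which is post-randomisation by definition.

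Elsewhere, Section 9 has three relevant statements:

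- Missing Data: "The primary outcome will be tested using an intent-to-treat framework".
- Statistical Analysis: a separate covariate rule for the primary analyses, limited to baseline variables.
- Primary Aim Analysis: a model with condition, linear time and their interaction, which may be expanded with covariates. Gender and era of service are given as examples; treatment as usual is not named.

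**The concern.** Care received after randomisation can be a consequence of drinking, and therefore of the study drug. The protocol sets up this link in three places:

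- At each prolonged exposure session the therapist looks for "increasing alcohol or other substance use that may necessitate referring the Veteran to a higher level of care" (Section 9, PE psychotherapy).
- When substance use worsens, Section 15 says: "If more intensive treatment is appropriate, we will assist the participant in obtaining the appropriate treatment".
- Section 9.9 provides for referral: "If treatment is needed during the follow-up phase due to increased alcohol consumption".

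If topiramate works as hypothesised, the arms may differ in later care because of the drug. A difference between arms is exactly what brings the variable into the model. Randomisation balances what precedes it, not what follows from treatment, so the expectation that changes will be similar across arms does not protect the analysis.

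The adjusted estimate can move either way. It shrinks if drinking drives extra care, because care then acts as a proxy for the outcome. It grows if extra care lowers drinking and is used less on topiramate, because adjustment then removes the cost of the lost care. The secondary efficacy models, also described as intent-to-treat, fall under the same wording.

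**Working it through.** **The plan's own figures.** Power analysis gives an effect of 0.406 SD; Section 10 gives 60 per arm. Alpha is not stated; 0.05 is assumed.

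- Two-tailed, 80% power: n per arm = 2(1.960 + 0.842)² / 0.406² = 95.2, so 96 per arm and N = 192, as stated.
- One-tailed at N = 120: 0.406 × √(60/2) = 2.224; 2.224 − 1.645 = 0.579; power 71.9% (exact t 71.4%), against the stated 72%.
- Two-tailed at N = 120, effect 0.516: 0.516 × √30 = 2.826; 2.826 − 1.960 = 0.866; power 80.7% (exact t 80.0%), as stated.

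**Assumptions.** The documents give no effect of care on drinking or of the drug on care, so what follows is illustrative: no missing data, one-tailed 5%, and the rule firing when a t-test on care gives p < 0.05.

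**Post-treatment comparison (the sizing basis; 20,000 runs).** T is the topiramate indicator, Y is drinking in SD units, and e and u are independent errors.

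*Drinking drives care:* Y = −0.406T + e; care = rY + √(1 − r²)u. If care were always adjusted for, the effect would be 0.406(1 − r²), which is 0.369, 0.305 and 0.260 for r = 0.3, 0.5 and 0.6. Because the rule fires only sometimes, the average moves less:

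| r | rule fires | mean effect | power (unadjusted 71%) |
|---|---|---|---|
| 0.3 | 10% | 0.39 | 70% |
| 0.5 | 19% | 0.36 | 65% |
| 0.6 | 27% | 0.33 | 61% |

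This scenario needs changes in care during treatment; referral in follow-up comes too late to affect the post-treatment comparison.

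*Care lowers drinking and is used less on topiramate:* care = −gT + u; Y = −(ITT + bg)T − b·care + e, with var(e) = 1 − b². If always adjusted for, the effect would be 0.406 + bg: 0.466, 0.526 and 0.606. Under the rule:

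| g, b | rule fires | mean effect | type I error at zero ITT effect |
|---|---|---|---|
| 0.2, 0.3 | 19% | 0.43 | 6.7% |
| 0.3, 0.4 | 38% | 0.48 | 11% |
| 0.4, 0.5 | 59% | 0.56 | 23% |

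The zero-effect case assumes a direct drug benefit of bg = 0.06, 0.12 or 0.20 SD, exactly offset by less care.

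**A different model as a cross-check.** With care as yes/no and the ITT effect held at 0.406:

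- Care in 20% against 40%, lowering drinking by 0.3 SD and unrelated to severity: adjusted effect 0.466, matching 0.406 + 0.3 × (0.40 − 0.20).
- Care driven by latent severity, about 24% against 42%: 0.384 if care lowers drinking by 0.3 SD, 0.332 if it has no effect.
- Care driven by latent severity, about 13% against 42%: 0.372 and 0.286 respectively.
- Care equal in both arms: 0.406, no distortion.

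**Group by time (the planned test; 4,000 runs).** This is a linear random-intercept approximation: four visits, outcome-error intraclass correlation 0.5, effect present at each post-baseline visit. The planned gamma/log-link model was not simulated. Entered as one time-constant covariate, care changes the interaction by 0%. Entered per visit, the ratio to the unadjusted estimate, across the three strengths above in order, is:

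| within-person correlation of care | care lowers drinking: ratio | type I error | drinking drives care: ratio |
|---|---|---|---|
| 0.9 | 1.03 / 1.11 / 1.29 | 6% / 9% / 20% | 0.98 / 0.89 / 0.80 |
| 0.5 | 1.05 / 1.16 / 1.38 | 7% / 12% / 26% | 0.98 / 0.91 / 0.85 |
| 0 | 1.10 / 1.26 / 1.48 | 8% / 15% / 31% | 0.97 / 0.89 / 0.81 |

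Unadjusted type I error in these runs was 4.8% to 5.3%.

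**Same trigger, pre-randomisation care only** (scenarios where care lowers drinking): mean post-treatment effect 0.40 to 0.41, type I error 4.4% to 5.1%, group by time ratio 1.000.

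**The case against.** The strongest reply is that the rule never reaches the primary test. It sits in a clinical-care paragraph. The statistical section admits only baseline variables to the primary analyses, and the primary model mentions covariates only as an expansion. On that reading the fault is an unstated time point and model, with the intent-to-treat test intact. It is a possible reading, and reach to the primary model remains an inference. But nothing says the baseline rule overrides the other, so the analyst has one limited and one unlimited rule to choose between, and the secondary models are exposed either way.

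Second, the simplest way of entering care leaves the linear group by time test unchanged, and the plan mentions time-varying covariates only for drinking and PTSD severity in exploratory models. This stands. The protection is not secured, however, because the plan does not say how care would enter.

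Third, the inflated type I errors come only from scenarios in which topiramate lowers care by a route other than drinking. If drinking alone drives care and the drug has no effect on drinking, that inflation does not arise, and under a real benefit the bias is toward the null. The stronger scenarios are also demanding: an exact offset under the null, or care uncorrelated within person when at least 85% are expected to be on guideline medication. These limits stand; the upper figures should be read as what the rule could permit, not as a forecast.

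Fourth, stable addiction medication and discontinuation for treatment counter to study criteria narrow the pathway. They do not close it: other psychotropic medication and psychotherapy can still change, and the plan is to collect post-randomisation data regardless of treatment attrition.

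**Conclusion.** The concern holds. As written, the rule allows adjustment for post-randomisation care when the arms differ on it, which conflicts with the intent-to-treat commitment. This conclusion follows from the text and does not depend on the simulations.

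The size is unknown. At the mild end the post-treatment effect is 0.39 or 0.43 against 0.406, with power 70% against 71%, or type I error 6.7% against 5%. At the strong end the distortion is material: an effect of 0.33 or 0.56, power 61%, type I error 23%. For the planned group by time test the range runs from no change to −20% or +48%, depending on how care is entered and on its within-person correlation. With planned power of only 72%, there is little room for avoidable loss. The change should be made; confidence is medium, because reach to the primary model is inferred and every magnitude is assumed.

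**What to change.** In Section 9, Standard Pharmacotherapy, state that covariates in the primary and secondary efficacy models are limited to variables measured before randomisation. Report treatment as usual after randomisation by arm, descriptively, and label any model that adjusts for it exploratory. Add one line to Statistical Analysis and one to Primary Aim Analysis so that the three places agree.

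The cost is wording only: no new data, no more participants, and the stated power figures are unchanged. The downside is that a visible difference in care between arms would be handled only in exploratory analyses.

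A separate, minor improvement, which is not a bias claim, is to replace the imbalance-triggered baseline covariates with a short pre-specified set that includes the stratification factor (anti-relapse medication). As main effects these leave the group by time estimate unchanged in a linear model with complete data.
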